the first 3 weeks of combination therapy (a medication diary will be provided during this time to monitor participant compliance: see Appendix F). All toxicities will be assessed upon completion of the first 6 evaluable patients to see if any higher than anticipated occurrence of sorafenib toxicity is seen due to the addition of pembrolizumab.

The goal of the study is to evaluate efficacy of the combination therapy, therefore patients who are removed from the study prior to receiving the soraf+pembro combination treatment will be replaced. This includes replacing patients who do not tolerate sorafenib alone, as administered in the 1st 4 - 6 weeks of the treatment regimen. In addition, the following patients will be replaced:

- Patient withdraws consent
- Withdrawal from study due to toxicity,
- Withdrawal from study due to liver failure
- Patients who withdraw before the Week 12 (± 1 week) response assessment (for reasons other than progression)

Patients who withdraw due to disease progression prior to the Week 12 (± 1 week) response assessment of the combination therapy will not be replaced and will be counted as non-responders in the response rate calculations.

Patients who complete the 4-6 week initial treatment with sorafenib alone, and withdraw from the study after being treated with the combination therapy will not be replaced and will be counted as non-responders in the response rate calculations.

Patients will receive sorafenib + pembrolizumab until progression. If a patient discontinues either agent due to toxicity, they will still be able to stay on study until progression. Clinical benefit will be considered when making decision to stop therapy as radiographic reflection of true failure of this combination is still unknown.

Disease assessment (imaging) will be done every 6 weeks from the start of C1D1 combination therapy, with a confirmatory assessment no less than 6 weeks after an irPR or irCR or irPD. Therapy will be continued until the confirmatory scan, even if progression is noted on the Week 12 scan. After the 12-week scan disease assessment will be done every 9 weeks (± 1 week). Note: Timing for assessing ORR in patients on immunotherapies is not clear. Disease stability is the commonly seen response to sorafenib alone. Allowing continuation until the confirmatory scan at Week 18, even if progression is seen, allows us to assess the true response to this novel combination.

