12.0 Withdrawal of Subjects

12.1 Treatment Discontinuation

Upon treatment discontinuation all end of treatment evaluations and tests will be conducted. All participants who discontinue due to an AE must be followed until the event resolves or stabilizes. Appropriate medical care should be provided until signs and symptoms have abated, stabilized, or until abnormal laboratory findings have returned to acceptable or pre-study limits. The final status of the AE will be reported in the participant's medical records and the appropriate eCRF.

Reasons for treatment discontinuation should be classified as follows:

- Death
- Progressive disease
- Toxicity; treatment related or unrelated
- Investigator judgment
- The Investigator may discontinue a participant if, in his/her judgment, it is in the best interest of the participant to do so.
- Noncompliance
- Participant voluntary withdrawal
 - A participant may withdraw from the study at any time, for any reason. If a participant discontinues treatment, an attempt should be made to obtain information regarding the reason for withdrawal

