Appendix E Schedule of Procedures

Trial Period	Screening	Sorafenib only	Combination (sorafenib + pembrolizumab) Treatment Cycles ³						End of Study ⁴	Post-Treatment		
			1	2	3	4	5	6 ^{3a}		Safety Follow-Up ⁵	Follow Up ⁶	Long Term Follow-Up ⁷
Phase Ib and Phase II:	Baseline¹	Day -28 to Day -1*										
Clinical Assessments												
Medical History and Pre-existing Conditions	X									X		
Prior and Concomitant Medication Review	X ⁸		X ⁹	X ⁹	X ⁹	X ⁹	X ⁹	X ⁹	X ⁹	X ⁹	X ⁹	
Physical Examination ¹⁰ ; including vital signs, body weight, & height ¹¹	X	X ²	X	X	X	X	X	X	X	X		
Child Pugh A	X											
ECOG Performance Status	X		X	X	X				X	X		
Adverse Events		X ²	X	X	X	X	X	X	X	X	X	
Survival Status			X	X	X	X	X	X		X	X	X
Laboratory Procedures												
Hematology: CBC with Differential ¹²	X	X ²	X	X	X	X	X	X	X	X		
Chemistry: CMP ¹³	X	X ²	X	X	X	X	X	X	X	X		
T3, FT4, and TSH ¹⁴	X						X		X	X		
Viral Titers: Hepatitis B and C ²² ; Hepatitis B Surface Antigen (HBsAg) and/or detectable HBV DNA and, Hepatitis C Antibody (anti-HCV)	X						X		X			

Trial Period	Screening	Sorafenib only	Combination (sorafenib + pembrolizumab) Treatment Cycles ³						End of Study ⁴	Post-Treatment		
			1	2	3	4	5	6 ^{3a}		Safety Follow-Up ⁵	Follow Up ⁶	Long Term Follow-Up ⁷
Phase Ib and Phase II:	Baseline¹	Day -28 to Day -1*	1	2	3	4	5	6 ^{3a}				
Ab), and detectable HCV RNA												
Coagulation ¹⁵	X											
Tumor Marker (AFP) ¹⁶	X			X		X			X			
Serum Pregnancy Test	X											
Imaging												
CT of chest, abdomen, and pelvis ¹⁷	X			X		X			X			
Study Drugs												
Sorafenib, po		X	X	X	X	X	X					
Pembrolizumab, IV			X	X	X	X	X	X				
Tumor Biopsies/Archival Tissue Collection/Correlative Studies Blood												
Archival Tissue Collection ¹⁸	X											
Tumor biopsy	X ¹⁸								X ¹⁹			
Correlative Studies Blood Collection ²⁰	X		X			X			X			
Pharmacokinetic Blood Sampling ²¹			X			X			X			

*The sorafenib lead in phase can extend up to Day-42 to Day-1 to allow stabilized dosing.

- 1 Within 28 days prior to start of sorafenib only study treatment (unless otherwise noted.)
- 2 Toxicity assessment within 2 weeks of starting sorafenib lead-in to include a directed physical exam and vitals.

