- 3 One cycle = 3 weeks (sorafenib + pembrolizumab). Pembrolizumab to be administered on Day 1 (\pm 3 days) of each 3-week cycle. Note: After Cycle 1 Day 1, all on-study visit procedures are allowed a window of \pm 3 days unless otherwise noted. 3a The number of cycles may vary (with each patient) and additional cycles may occur, as clinically indicated. After a patient has been on pembrolizumab for more than 24 months the PI can decide if the patient can come off pembrolizumab and continue on with sorafenib treatment.

- 4 End of study or, at time decision is made to discontinue treatment (e.g. toxicity, physician decision, or patient withdraws consent).
- 5 Safety follow up to be conducted approximately 30 days (\pm 3 days) after last dose of trial treatment, or until resolution of any drug-related toxicity or before the initiation of a new anti-cancer treatment, whichever comes first.
- 6 Participants who discontinue treatment for other than disease progression will move into the follow-up phase: assessments every 3 months for 1 year or until death. Telephone contact is acceptable.
- 7 All patients will be followed by medical review every 6 months for survival.
- 8 List any medications that are ongoing, or that will be discontinued, within 1 week prior to first dose of study drug (refer to Section 10.3 for Acceptable and Prohibited concomitant medications). All concomitant medications received within 28 days before the first dose of trial treatment and 30 days after that last dose of trial treatment should be recorded.
- 9 List any ongoing medications with dose changes, as applicable. Concomitant medications administered after 30 days after the last dose of trial treatment should be recorded for SAEs and ECIs as defined in Section 17.0.
- 10 A physical exam within 1 week of consent is acceptable.
- 11 Vital signs (temperature, heart rate, respiratory rate, blood pressure), body weight and height. Height collected at baseline only.

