2.6 Confirmation Measurement

A confirmatory assessment is required no less than 6 weeks after an irPR or irCR is deemed by irRECIST (14)

3 Guidelines for Evaluation of Measurable Disease

All measurements should be taken and recorded in metric notation. All baseline evaluations should be performed as closely as possible to the beginning of treatment and never more than 4 weeks before the beginning of the treatment.

The same method of assessment and the same technique should be used to characterize each identified and reported lesion at baseline and during follow-up. Imaging-based evaluation is preferred to evaluation by clinical examination unless the lesion(s) being followed cannot be imaged but are assessable by clinical exam. The preferred imaging modality for this clinical trial is conventional CT scan using IV contrast.

- **Clinical Lesions:** Clinical lesions will only be considered measurable when they are superficial (e.g., skin nodules and palpable lymph nodes) and ≥ 10 mm diameter as assessed using calipers (e.g., skin nodules). In the case of skin lesions, documentation by color photography, including a ruler to estimate the size of the lesion, is recommended.
- **Chest x-ray:** Chest x-ray is not accurate in assessment of lesion size in the lung and should not be used as a method of measurement. Conventional chest CT is the preferred imaging modality to evaluate response to treatment.

- **Conventional CT and MRI:** This guideline has defined measurability of lesions on CT scan based on the assumption that CT slice thickness is 5 mm or less. If CT scans have slice thickness greater than 5 mm, the minimum size for a measurable lesion should be twice the slice thickness. MRI is also acceptable in certain situations (e.g., for body scans) however, conventional CT scan is the preferred modality to determine response to treatment.

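### Section 9.1 both replaces and counts as non-responders the combination-treated patients who withdraw for toxicity, liver failure or withdrawn consent, and the endpoint sections do not settle how a withdrawn responder counts towards 4 of 27

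*Combined protocol and SAP*

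**What the plan says.** **Replacement list (section 9.1).** After providing for patients who leave before the combination starts, including those who do not tolerate sorafenib alone, the section continues "In addition, the following patients will be replaced". The list has four entries: withdrawn consent, "Withdrawal from study due to toxicity", withdrawal for liver failure, and withdrawal before the Week 12 assessment for reasons other than progression. Only the fourth has a time limit.

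**Non-responder rules (section 9.1).** Patients who progress and withdraw before the Week 12 assessment stay in and count as failures. A later paragraph says that patients who finish the sorafenib lead-in and "withdraw from the study after being treated with the combination therapy will not be replaced and will be counted as non-responders". It gives no exception by reason or by time.

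**Staying on study (section 9.1).** A patient who stops either agent for toxicity may remain on study until progression.

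**Endpoint (sections 8.0, 19.0, 19.3).** ORR is the share of evaluable patients with a complete or partial response by irRECIST within 6 months of starting the combination. None of the three sections mentions confirmation. Appendix H 2.6 does: "A confirmatory assessment is required no less than 6 weeks after an irPR or irCR is deemed by irRECIST". Section 9.1 gives the same interval.

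**Imaging (Appendix E, section 12.1).** The row "CT of chest, abdomen, and pelvis" is marked at screening, Cycle 2, Cycle 4 and End of Study, and footnote 17 adds scans every 9 weeks. The three post-treatment columns are blank. Footnote 4 sets the End of Study visit as "End of study or, at time decision is made to discontinue treatment", and section 12.1 agrees: "Upon treatment discontinuation all end of treatment evaluations and tests will be conducted". Patients who stop for reasons other than progression then have "assessments every 3 months for 1 year or until death. Telephone contact is acceptable" (footnote 6).

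**Decision rule (section 19.1).** The treatment is deemed effective with 4 or more responders among 27 evaluable patients.

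**The concern.** A patient who has received the combination and withdraws from the study for toxicity satisfies both 9.1 rules. One takes the patient out of the 27 and brings in someone new; the other keeps the patient as a failure. No order of precedence is given. The conflict is the same for liver failure, for withdrawn consent, and for any other non-progression withdrawal before Week 12.

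If that patient already had an irPR or irCR, section 19.0 can be read as giving a third result, a responder. Whether it does depends on whether confirmation belongs to the primary endpoint, which is not stated. For a response first seen less than 6 weeks before treatment stops, the End of Study CT comes too early to confirm it and no later CT is scheduled.

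The trial is open-label and its conclusion turns on a count of 4. With two rules on the page, the choice could be made after the patient's response is known. Replacement also changes the population to which the 5% null applies.

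**Working it through.** **Inputs.** From section 19.1: null ORR 0.05, target ORR 0.20, 27 evaluable patients, success at 4 or more, 5% type I error, 80% power. The share of treated patients who withdraw and are replaced is not in the documents; I call it w and show a range.

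**1. The plan's own design.** With X ~ Binomial(27, p):
- Type I error: P(X ≥ 4 | 0.05) = 1 − (0.2503 + 0.3558 + 0.2434 + 0.1068) = 0.0437.
- Power: P(X ≥ 4 | 0.20) = 1 − (0.0024 + 0.0163 + 0.0530 + 0.1105) = 0.818.

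The design reproduces, and 27 is the smallest sample size meeting both limits.

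**2. One patient at the boundary.** Suppose 3 responders among the other 26, and a 27th patient with a documented irPR at Week 12 who withdraws from the study for toxicity at Week 15. The End of Study CT is 15 − 12 = 3 weeks after the response, short of 6.

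| Reading | Count | Estimate (Jeffreys 95% CI) | Exact tail at 5% null | Decision |
|---|---|---|---|---|
| 19.0, first response counts | 4/27 | 14.8% (5.2% to 31.5%) | 0.0437 | effective |
| 9.1, later paragraph | 3/27 | 11.1% (3.2% to 26.8%) | 0.0437 + 0.1068 = 0.1505 | not effective |
| 9.1, replacement list | 3/26 plus a new patient | open | open | rests on the new patient, who responds with probability 0.20 if the true ORR is 0.20 |

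If the withdrawing patient had no response, the first row falls away and the other two still conflict.

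**3. Effect of replacement on type I error.** Let the null ORR be 0.05 among all patients who start the combination. If a share w of them withdraw without a response and are replaced, the ORR among the 27 is 0.05/(1 − w).
- w = 10%: 0.05/0.90 = 0.0556, and P(X ≥ 4) = 0.060.
- w = 20%: 0.05/0.80 = 0.0625, and P(X ≥ 4) = 0.085.
- P(X ≥ 4) reaches 0.05 at an ORR of 0.0522, that is w = 1 − 0.05/0.0522 ≈ 4.3%.

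These figures assume that no replaced patient is a responder. If withdrawal is unrelated to response, the ORR among the 27 stays at 0.05 and type I error at 0.0437.

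As context for w, section 4.0 accrues 41 for 27 evaluable, which leaves room for 14 of 41 (34%) not to be evaluable. How many of those would leave after the combination starts is not given.

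**The case against.** **The two 9.1 rules may have been meant for different periods.** The list could be confined to the sorafenib lead-in, or to the time before Week 12, with the later paragraph applying afterwards. The lead-in reading fails: lead-in intolerance is dealt with in the preceding sentence, the list is introduced as an addition, and its last entry refers to the Week 12 assessment. The Week 12 split is a plausible intention, but three of the four entries carry no time limit and the later paragraph has no starting point after the first combination dose. Even under that split, early non-responding withdrawals would be replaced, and step 3 would still apply to them.

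**The responder reading of 19.0 rests on silence.** Sections 8.0 and 19.0 refer to irRECIST, section 16.1 sends the reader to Appendix H, and Appendix H requires confirmation. Read together, an unconfirmed response may simply not count, leaving two outcomes instead of three. This stands, so the third outcome is only a possible reading. The clash inside 9.1 does not depend on it.

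**A reader might infer that nothing is imaged once treatment stops, or that every responder who stops falls into the conflict.** The documents do not support either. The End of Study CT can confirm a response first seen at least 6 weeks before. A patient who stops only one agent may stay on study, where the 9-weekly scans continue and neither withdrawal rule applies. After Week 12, a withdrawal for a reason outside the list is not subject to replacement.

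**A reader might infer that type I error is certainly above 5%.** It need not be. Progression before Week 12 is expressly not replaced, which removes an obvious group of non-responders from step 3, and the inflation needs the remaining withdrawals to be mostly non-responders.

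**Conclusion.** The point holds in a limited form. Section 9.1 cannot be applied as written to a combination-treated patient who withdraws from the study for toxicity, liver failure or withdrawn consent, or before Week 12 for another non-progression reason. For a withdrawn patient with a documented response, the plan also leaves open whether an unconfirmed response counts.

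One such patient decides the result when the count among the other 26 is 3. The effect on type I error is conditional: 0.060 at an assumed 10% replaced with no responders among them, above 0.05 from about 4.3%, and no change if withdrawal is unrelated to response. The documents give no frequency for these withdrawals, so how often the decision would change cannot be estimated from them.

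The sample size and threshold are not in error: with all treated patients kept in the 27 and first responses counted, type I error is 0.0437 and power 0.818.

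**What to change.** 1. In section 9.1, put one rule in place of the two. Suggested: replacement only for patients who never start combination therapy; every patient who starts it stays in the 27, whatever the reason for leaving.
2. In sections 8.0, 19.0 and 19.3, state whether ORR counts confirmed or first responses and how a response without a confirming scan is counted. Report the other count as a sensitivity analysis.
3. Make the meaning of evaluable in sections 4.0 and 19.1 agree with this rule. The criterion of more than 75% of prescribed sorafenib in section 9.1 sits within the early toxicity text and is not tied to the 27.

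A CT after treatment stops, at least 6 weeks after a first response, would let more responses be confirmed. It is optional: the counting can be settled without it.

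**Cost.** This is a wording amendment with no new procedure, and it needs no more accrual than planned, since fewer patients are replaced. The expected ORR among the 27 is somewhat lower than with replacement. For illustration, take 10% of treated patients withdrawing without a response. If the 0.20 target refers to all treated patients, power stays at 0.818. If it was meant for the patients who remain, the ORR among all treated is 0.20 × 0.90 = 0.18 and power is 0.742; the sponsor should say which was intended.

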Appendix J Guidance for Diagnosis and Management of Hepatic Events of Clinical Interest

In addition to overdose, hepatic events of clinical interest (ECIs) will include any of the following events. All of these events will require holding study treatment until the patient no longer meets the criteria below. Notification of events to Roswell Park within 24 hours is required. Refer to Section 17.4 for reporting guidelines and the definition of hepatic ECIs. Roswell Park will report within 2 working days to Merck Global safety.

All cases of retreatment and permanent discontinuation must be reported to the Sponsor and recorded in the database.

- a) ALT:
 - i) Among subjects with baseline ALT < 2 x ULN: ALT \geq 5 x ULN
 - ii) Among subjects with baseline ALT \geq 2 x ULN: ALT > 3 x the baseline level
 - iii) ALT > 500 U/L regardless of baseline level
- b) AST:
 - i) Among subjects with baseline AST < 2xULN: AST \geq 5 x ULN
 - ii) Among subjects with baseline AST \geq 2 x ULN: AST > 3 x the baseline level
 - iii) AST > 500 U/L regardless of baseline level
- c) Total Bilirubin:
 - i) Among subjects with baseline levels < 1.5 mg/dL: a value of > 2 mg/dL
 - ii) Among subjects with baseline levels that are \geq 1.5mg/dL: a value \geq 2 x the baseline level
 - iii) Total bilirubin > 3.0 mg/dL regardless of baseline level
- d) Regardless of laboratory values, hepatic decompensation diagnosed clinically, including:
 - i) New onset clinically detectable ascites
 - ii) Gastrointestinal bleeding suggestive of portal hypertension (e.g., esophageal or gastric varices)
 - iii) Hepatic Encephalopathy

Immediate assessment

All subjects

- All subjects should be evaluated according to directions below within 72 hours of alert for non-overdose ECI
- Procedures:
 - Obtain a work-up for hepatitis if there is no underlying hepatitis, including hepatitis A, B, C, D, E, Epstein-Barr virus, and cytomegalovirus
 - Assess for ingestion of drugs/supplements with hepatotoxic potential
 - Assess for alcohol ingestion

Roswell Park Protocol No.: I 35316

- Assess for potential bacterial infection, biliary obstruction, or occult gastrointestinal bleeding
- Repeat ALT, AST, total bilirubin (Tbil), direct bilirubin (Dbil), alkaline phosphatase (ALP), γ -glutamyl transpeptidase (GGT), INR, and complete blood count (CBC) with differential
- Other laboratories or imaging studies as clinically indicated
- Consider liver biopsy if indicated

Hepatitis C-Infected Subjects (including subjects who previously achieved SVR 12)

- In addition to the above, measure HCV RNA viral load

Hepatitis B-infected Subjects

- HBV DNA, HBsAg, HBeAg, anti-HBc (total and IgM), anti-HBe, and anti-HBs
- Subjects should be questioned about compliance with the use of anti-viral agents

Permanent Discontinuation Criteria for Subjects with Non-overdose Hepatic ECI

Therapy should also be permanently discontinued for any of the following:

- ALT $> 20 \times$ ULN
- CP score of ≥ 9 points
- Gastrointestinal bleeding suggestive of portal hypertension (e.g., esophageal or gastric varices)
- New onset of clinically detectable ascites
- Hepatic Encephalopathy
- Recurrence of a severe or life-threatening event, or of any of the laboratory abnormalities listed above, that are presumed to be immune-related

Diagnosis and Management of Non-Overdose Hepatic ECIs

HCC patients are at risk for a range of complications that can cause hepatic laboratory abnormalities with or without clinical decompensation. Those with a history of chronic HCV or HBV infection also have the potential to experience virologic flares. Immune-related hepatitis has been observed in approximately 1% of subjects who received pembrolizumab. The following section provides further guidance on the diagnosis and management of potential hepatic complications among HCC subjects in this study.

a) Hepatitis B Flare

Hepatitis B flares are characterized by rapid elevations of ALT and AST to $> 5 \times$ ULN and/or $> 3 \times$ baseline. ALT elevation to $\geq 10 \times$ ULN is common. In the absence of hepatic decompensation, ALT/AST elevations are typically isolated (i.e., limited/no elevations of bilirubin/ALP). Subjects who are compliant with anti-viral therapy should have continued suppression of HBV DNA at the time of flare; thus, detection of HBV DNA should prompt questioning of subjects for compliance. Laboratory abnormalities secondary to flare are typically observed for 3-5 weeks.

Among subjects with HBV, a flare should be considered if this pattern is observed and there is

Roswell Park Protocol No.: I 35316

no evidence of an alternative etiology. Guidelines for subjects with a diagnosis of HBV flare are no evidence of an alternative etiology; Guidelines for subjects with a diagnosis of HBV flare are as follows:

- Care should be instituted in consultation with a hepatologist if available.
- For subjects who have detectable HBV DNA, re-institute anti-viral therapy.
- If the subject is clinically stable, study treatment dosing may be interrupted for up to 12 weeks. Subjects should undergo weekly laboratory tests including: AST, ALT, ALP, Tbil, Dbil, INR, HBsAg and, HBV DNA (if detected at the onset of the flare). Obtain anti-HBe, anti-HBs, and HBV DNA levels (if not detected at the onset of the flare) every 2-3 weeks.
- If ALT returns to normal or Grade 1 (if normal at baseline), or to baseline grade (if Grade 2 at baseline) within 12 weeks, and subjects are clinically stable, subjects may restart study treatment. If these conditions are not met, then study treatment should be permanently discontinued.

b) Hepatitis C Recurrence or Flare

Subjects who achieved SVR 12 and subjects with ongoing HCV infection are eligible for enrollment. In rare circumstances, HCV subjects who achieve SVR 12 may relapse at later time points. Relapse is characterized by detection of HCV RNA, often accompanied by ALT elevations to $> 5 \times$ ULN. In the absence of hepatic decompensation, ALT/AST elevations are typically isolated (i.e., limited/no elevations of bilirubin/ALP).

Among subjects with uncontrolled hepatitis C, virologic flares are possible. Hepatitis C flares are characterized by rapid elevations of ALT and AST to $> 5 \times$ ULN and/or $> 3 \times$ baseline along with a rise in HCV RNA. ALT elevation to $\geq 10 \times$ ULN and a 1 log elevation in HCV RNA level are common. In the absence of hepatic decompensation, ALT/AST elevations are typically isolated (i.e., limited/no elevations of bilirubin/ ALP). Laboratory abnormalities secondary to flare or recurrence are typically observed for 3-5 weeks.

Guidelines for subjects with recurrent HCV infection or an HCV flare are described below:

i) Recurrent HCV infection:

If the subject entered the study with an HCV RNA test of "Target not Detected" and has confirmed detectable HCV RNA (2 specimens, 1 week apart), then the subject has experienced a late HCV relapse or a recurrent infection.

- Question the subject about use of injection or inhalation drugs
- At the time of first detection of HCV RNA, send a specimen for HCV genotyping
- Measure AST, ALT, ALP, Tbil, Dbil, and INR weekly
- Measure HCV RNA levels every 2 weeks
- Therapy with HCV anti-viral treatments should be strongly considered.

ii) HCV Flare:

- At the time of first detection of HCV RNA, send a specimen for HCV genotyping

Roswell Park Protocol No.: I 35316

- Measure AST, ALT, ALP, Tbil, Dbil, INR weekly
- Measure HCV RNA levels every 2 weeks
- Therapy with HCV anti-viral treatments should be strongly considered.

iii) For both recurrent infection and HCV flare: if ALT returns to normal or Grade 1 (if normal at baseline), or to baseline grade (if Grade 2 at baseline) within 12 weeks, and the subjects are clinically stable, subjects may restart study treatment. If these conditions are not met, then study treatment should be permanently discontinued.

c) Immune-related hepatitis

i) Description: Immune-related hepatitis due to study treatment should be suspected if any of the following is seen:

- AST or ALT baseline values are less than 2 x ULN, and AST or ALT laboratory values increase to ≥ 5 x ULN
- Among subjects with baseline ALT or AST ≥ 2 x ULN, levels increase to > 3 x the baseline level
- AST/ALT >500 U/L regardless of baseline level
- Among subjects with baseline Tbil levels < 1.5 mg/dL: a value of > 2 mg/dL
- Among subjects with baseline Tbil levels that are ≥ 1.5 mg/dL: a value of ≥ 2 x the baseline level
- Total bilirubin > 3.0 mg/dL regardless of baseline level.

Immune-related hepatitis is a diagnosis made after excluding other possible etiologies for the change. Viral flare (if applicable), biliary or vascular obstruction, infection, medications, and alcohol use must be ruled out (see below).

ii) Management

- Interrupt study treatment and alert the Sponsor as per ECI criteria above for ALT, AST, bilirubin, and hepatic decompensation.
- Start IV corticosteroid (methylprednisolone: 125 mg or equivalent) followed by oral corticosteroid.
- Monitor with biweekly laboratory tests including AST, ALT, Tbil, Dbil, ALP, and INR.
- If symptoms and laboratory tests resolve to Grade ≤ 1 or baseline (if abnormal at baseline), taper steroids over 28 days. Study treatment may be restarted after steroid treatment has been tapered to prednisone ≤ 10 mg/day (or equivalent dose of another agent). Treatment and laboratory results must be reported on a case report form (CRF).
- If laboratory abnormalities do not resolve within 3 weeks, or steroids cannot be lowered to ≤ 10 mg/day (or prednisone equivalent) within 12 weeks, or subjects show evidence of decompensation to CP C status or have esophageal or variceal bleeding at any point, treatment must be permanently discontinued.

This must be reported on a CRF.

d) Other Hepatic Events of Clinical Interest

- Infection needs to be ruled out with cultures of blood, urine, and ascites (if possible), as well as chest X-ray and abdominal imaging if relevant. If an infection is found, antibiotics should be started.
- If Tbil is elevated above baseline, magnetic resonance cholangiopancreatography or ultrasound with Doppler should be obtained to rule out vascular compromise, biliary obstruction, and/or tumor progression. If biliary obstruction is present, consultation with a gastroenterologist and/or an interventional radiologist should be obtained to see if the obstruction may be relieved.
- A careful review of drugs, including herbal and alternative medications, should be obtained, and alcohol use should be ruled out.
 - Drugs known to be hepatotoxic (i.e., drugs with a warning of hepatotoxicity in the package insert) should be avoided during the dosing period. Investigators are encouraged to review each medication for potential hepatotoxicity by searching the www.livertox.nih.gov website.
- For all of these cases, subjects may resume study treatment if they are clinically stable after appropriate therapy or discontinue the causative agent, as long as laboratory values have returned to Grade 1 or baseline (if normal or Grade 1 at start) or to baseline grade within 3 weeks.
- Treatment must be permanently discontinued if the subject is off study treatment therapy for infection, obstruction, or drug/alcohol-related toxicity for more than 3 weeks, or if they have esophageal bleeding, or become CP C at any point.

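### Minor drafting gap: after a hepatitis B or C flare, the restart rule omits Grade 1 baseline ALT, so a stable patient back at Grade 1 is told to stop permanently

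*Combined protocol and SAP*

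**What the plan says.** All references are to the combined protocol and SAP, Appendix J, under diagnosis and management of non-overdose hepatic events of clinical interest.

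- **Part a), hepatitis B flare.** Dosing may be interrupted for up to 12 weeks in a clinically stable patient. Restart is allowed as follows: "If ALT returns to normal or Grade 1 (if normal at baseline), or to baseline grade (if Grade 2 at baseline) within 12 weeks", provided the patient is clinically stable. The next sentence reads: "If these conditions are not met, then study treatment should be permanently discontinued".
- **Part b) iii), hepatitis C recurrence and flare.** The condition is the same: "if ALT returns to normal or Grade 1 (if normal at baseline), or to baseline grade (if Grade 2 at baseline"). It carries the same 12-week limit, stability condition and discontinuation sentence.
- **Part c) ii), immune-related hepatitis.** The laboratory threshold is worded differently: "If symptoms and laboratory tests resolve to Grade ≤ 1 or baseline (if abnormal at baseline), taper steroids over 28 days".
- **Part d), other hepatic events.** Treatment may resume in stable patients whose laboratory values have "returned to Grade 1 or baseline (if normal or Grade 1 at start) or to baseline grade within 3 weeks".

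On who can enter, Section 3.1 allows AST and ALT up to 5 times the upper limit of normal (criterion 6), past or ongoing hepatitis C (criterion 11) and controlled hepatitis B (criterion 12).

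**The concern.** The flare rule ties recovery to Grade 1 to a normal baseline, and recovery to baseline grade to a Grade 2 baseline. A Grade 1 baseline lies between the two and is in neither clause. Because the rule ends with a default of permanent discontinuation, the omission decides the outcome for that patient.

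What is at stake is treatment management. A clinically stable patient whose ALT is back at its pre-study grade could lose study treatment because a category was left out. Sites reading the same text could also handle the same patient differently. No estimate or test in Section 19.0 depends on this rule.

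**Working it through.** The plan gives no figure to reproduce here and no arithmetic decides the point. The check sets each baseline grade against the two restart clauses in parts a) and b) iii), for a patient who is clinically stable within 12 weeks.

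| Baseline ALT | ALT after the flare | Clause that applies | Result as written |
|---|---|---|---|
| Normal | Grade 1 | First clause (Grade 1, normal baseline) | May restart, one grade above own baseline |
| Grade 1 | Grade 1 | First clause needs a normal baseline; second needs a Grade 2 baseline | No clause met; permanent discontinuation |
| Grade 2 | Grade 2 | Second clause (baseline grade, Grade 2 baseline) | May restart, at a higher grade than the patient above |

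**Does the grammar matter?** The first parenthesis, on normal baseline, can be read as qualifying only Grade 1 or as qualifying both normal and Grade 1. Either way, Grade 1 recovery is tied to a normal baseline, so the middle row does not change.

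**Can such a patient exist?** Section 3.1 admits raised ALT together with hepatitis B or C. The rule itself provides for baselines up to Grade 2, so a Grade 1 baseline is within its range. The documents refer to CTCAE version 4 but do not print the ALT limits, so nothing is claimed about baselines above Grade 2.

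**Can recovery fall inside the window?** For hepatitis B, part a) says: "Laboratory abnormalities secondary to flare are typically observed for 3-5 weeks". Part b) gives the same 3 to 5 weeks for hepatitis C. Against a 12-week limit that leaves 12 − 5 = 7 weeks even at the longer end, so return to baseline in time is an ordinary course of events.

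**Does another rule fill the gap?** Section 17.4 and the opening of Appendix J hold treatment until the event criteria are no longer met. That is a general rule. It contains no grade-based restart clause and does not cancel the flare-specific discontinuation sentence.

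**How do the neighbouring parts treat a Grade 1 baseline?** Part c)'s threshold is met at Grade 1 or below whatever the baseline. Part d) names a Grade 1 start. This compares wording only, because the surrounding conditions differ:

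- In part c) the threshold starts a steroid taper. Restart waits until prednisone is at 10 mg/day or less, and laboratory abnormalities that do not resolve within 3 weeks mean permanent discontinuation.
- Part d) allows 3 weeks, not 12, and requires stopping if the patient is "off study treatment therapy for infection, obstruction, or drug/alcohol-related toxicity for more than 3 weeks".

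So it does not follow that the same flare patient would have been allowed to restart under c) or d). What follows is that the authors provided for a Grade 1 baseline elsewhere in the same appendix.

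**The case against.** The strongest case on the other side is that this makes little practical difference. Appendix J is headed "Guidance for Diagnosis and Management of Hepatic Events of Clinical Interest", the default says *should*, and part a) asks for a hepatologist's involvement where one is available. The general hold rule shows the intent that treatment resumes once the event has settled, and a patient back at baseline ALT would ordinarily no longer meet the ALT event criteria. Hepatitis B must be controlled at entry, with viral load below 100 IU/mL. For hepatitis C, part b) says antivirals should be strongly considered, while Section 10.3 prohibits them during combination therapy and says patients who need prohibited treatment should be removed. That may settle the matter before the ALT grade does. Section 9.1 also lets a patient who stops either agent for toxicity stay on study until progression.

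All of this stands, and it is why the point is minor. It does not close the gap. An investigator who allows restart at Grade 1 from a Grade 1 baseline does so against the written default.

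A reader might infer more than the documents support:

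- **That a Grade 2-baseline patient who improves to Grade 1 is shut out in the same way.** The words omit that case only on a strict reading. ALT falling from flare level to Grade 1 has already returned to the Grade 2 baseline grade and passed below it, and a sensible reader would treat better than baseline as meeting the rule.
- **That a patient whose ALT becomes normal must stop unless baseline was normal.** This needs a still stricter reading of the first parenthesis that nobody would apply.
- **That the difference is known to be medically unjustified.** The documents give no rationale for the thresholds in either direction. The supportable statement is that they give no safety reason for it.

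**Conclusion.** The point holds for one case: Grade 1 baseline ALT with return to Grade 1 within 12 weeks in a clinically stable patient, after a hepatitis B flare or hepatitis C recurrence or flare. Followed as written, the rule discontinues that patient permanently, while allowing restart at Grade 1 from a normal baseline and at Grade 2 from a Grade 2 baseline. An omission is the more plausible explanation than a deliberate choice, given the wording of parts c) and d).

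Severity is minor. The documents give no rate for baseline ALT grade, flare or recovery, so no patient count or shift in the response rate can be derived; few or none of the 41 planned participants is the reasonable expectation. Sample size, alpha and power are unaffected. The conclusion rests on a literal reading of the two clauses and the default, and on eligibility admitting patients with raised ALT and viral hepatitis.

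**What to change.** In Appendix J a) and b) iii), reword the ALT condition along these lines: *ALT has come back, within 12 weeks, to Grade 1 or better where baseline was normal or Grade 1, or to the baseline grade or better where baseline was Grade 2*. Keep the 12-week limit, the clinical-stability condition and the discontinuation default. The substantive change is adding Grade 1 to the first baseline category; *or better* is a clarification only. Restart above a patient's own baseline grade would still be possible only from normal to Grade 1, as now.

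Then look once through the permanent discontinuations, which Appendix J already requires to be reported and recorded, for any patient stopped under the current text.

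The cost is a few words in two places at the next amendment and that one check. No extra procedures, patients or analyses are needed.
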